# **Dosing Rules for Stage 1:**

- 1) If fewer than 2 subjects experience DLTs, then the following scheme will be considered for Stage 2 dosing:
  - a. If fewer than or equal to 2 of the evaluable subjects have a response (as tumor volume PCFB complete response [CR], strong response [SR] or partial response [PR])) the dose will be escalated from 3 to 5 treatment applications per treatment visit for Stage 2.
  - b. If 3 or more evaluable subjects have a response (as tumor volume PCFB complete response [CR], strong response [SR] or partial response [PR])), the dose will remain the same for Stage 2 (3 applications per treatment visit).
- 2) If 2 or more subjects experience DLTs at any time during Stage 1, the following scheme will be considered for dose de-escalation in Stage 2:
  - a. If there are 5 evaluable subjects in Stage 1:
    - If out of 5 evaluable subjects, 2 or more subjects have a response (as tumor volume PCFB complete response [CR], strong response [SR] or partial response [PR])), the dose will be de-escalated to 2 applications per treatment visit.
    - If out of 5 evaluable subjects, fewer than 2 have a response (as tumor volume PCFB complete response [CR], strong response [SR] or partial response [PR])), the dose will be considered intolerable and the study will be stopped.
  - b. If Stage 1 dosing was stopped prior to having 5 evaluable subjects, the dose will be de-escalated from 3 applications to 2 applications per treatment visit.

#### c.

#### Figure 2. Stage 1 dose determination scheme

d) Target Dose for Stage 2a

*Stage 2:* In case of dose escalation or de-escalation, Stage 2 will be conducted in 2 parts: Stage 2a and Stage 2b.

Subjects will receive 2, 3, or 5 treatment applications at each of the 4 planned treatment visits, depending on the results of Stage 1. Up to 21 additional subjects will be enrolled in Stage 2 if necessary, for the purpose of 11 total evaluable subjects at the final dose for the efficacy analysis.

#### Stage 2a:

This stage will include 5 subjects (Stage 2a flowcharts). In this stage, only safety outcomes will be considered for determining the dosing regimen for the set of subjects to be enrolled in Stage 2b. All subjects enrolled in this stage will be monitored for possible DLTs.

- 1) If fewer than 2 subjects with DLTs in Stage 2a, enrollment will continue for the remaining number of subjects required in Stage 2b at the same dose.
- 2) If 2 subjects experience DLTs in Stage 2a, dosing will be re-considered. It may be stopped or, when possible, decreased for the remaining subjects enrolled in Stage 2b:
  - a. If "Stage 2a Escalated Dose", the original dose will be used on the remaining patients.

b. If "Stage 2a - De-escalated Dose", the study will stop, as no safe dose could be determined.

a) Stage 2a Enrollment Goal: 5 subjects
b) 2 subjects with DLTs, evaluated based on Safety Subjects
c) Target dose for Stage 2b

Figure 3. Stage 2a safety scheme in case of escalated dose decision

Figure 4. Stage 2a safety scheme in case of de-escalated dose decision

**Stage 2b:** In this stage both safety and efficacy will be evaluated. All subjects will be monitored for possible DLTs (Stage 2b – All Doses flowchart).

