# 6 INVESTIGATIONAL PLAN

# 6.1 Overall Trial Design and Plan: Description

*Study Design:* This is a 2-stage adaptive study. For Stage 1, up to 10 subjects will be enrolled for the purpose of 5 evaluable subjects for the 1st stage of the study to determine a safe and efficacious dose. For Stage 2, the target goal is 11 evaluable subjects for the efficacy analysis of the final dose. If the dose remains the same as Stage 1, Stage 2 will target 6 additional evaluable subjects but up to 21 subjects will be recruited if the dose is changed between Stage 1 and 2.

For the purpose of dose selection, tolerable dose is defined as a dose where fewer than 33% of subjects being evaluated within the safety population present with DLTs. Effective dose is determined based on the evaluable population as described in the Section 10.2.

The 2 stages of the study are described below:

*Stage 1:* Up to 10 subjects will be enrolled for the purpose of 5 evaluable subjects and undergo 3 treatment applications at each of the 4 planned treatment visits. Each treatment visit will involve application of 1 ml of the permeation enhancer and will be applied pre and post patch application (see Pharmacy Manual for details) (One ml vial of PE per visit, see Pharmacy Manual). Starting approximately 5 minutes after application of the PE, 1 or 2 patches (depending on tumor size) will be applied. A total of 3 treatment applications of patches will occur. These successive applications will span approximately 35 minutes. The 3 applications provide a total of 6 mg of cisplatin per visit (12 mg if 2 patches are applied at the same time). The 4 treatment visits will be separated by 2 to 6 days (at least 48 hours apart).

The following decisions will be made based on safety and efficacy of the dose:

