#### 7.7 Replacement of Subjects

Subjects will not be replaced.

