#### 10.3 Note: If the dose is not increased after Stage 1, the test will be performed using all evaluable subjects from Stage 1 and 2. If the dose is adjusted after Stage 1, the test will be performed using all evaluable subjects from Stage 2.Pharmacokinetics

#### **10.4 Study Populations**

#### 10.4.1 Safety Population

All subjects who have at least 1 PRV111 patch applied will be included in the Safety Population.

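### Stage 2a counts a subject who leaves early for a non-toxicity reason as a full subject without a DLT, so a changed dose can be cleared on fewer than five informative subjects

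*Protocol*

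**What the plan says.** Protocol 6.1 uses Stage 2a only when the dose changes after Stage 1. The legend to its flowcharts reads "Stage 2a Enrollment Goal: 5 subjects" and gives the trigger as "2 subjects with DLTs, evaluated based on Safety Subjects". The rule for going on is "If fewer than 2 subjects with DLTs in Stage 2a, enrollment will continue" at the same dose.

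The set behind that count is defined in Protocol 10.4.1: "All subjects who have at least 1 PRV111 patch applied will be included in the Safety Population". SAP 5.3.1 agrees. Protocol 7.7 states "Subjects will not be replaced", and SAP 2.8 and 6.3 say the same. The overall tolerability criterion in Protocol 6.1 uses the same set: "tolerable dose is defined as a dose where fewer than 33% of subjects being evaluated within the safety population present with DLTs".

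The only minimum-exposure rule is 75% of the stage dose, which SAP 5.2.2 reads as three of the four treatment visits. It defines the Evaluable Population, which is used for efficacy (Protocol 10.4.2). Neither document's text defines a DLT-evaluable set.

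Four other provisions bear on the point:
- Protocol 8.4 ends the DLT period 14 days after the last application, or at surgery if that is earlier.
- Protocol 8.2 makes any toxicity that prevents three of the four planned applications a DLT. SAP 2.10 restricts this to grade 3 or 4 toxicity related to the drug.
- Protocol 6.1 stops dosing in Stage 2b at 3 subjects with DLTs.
- SAP 2.2 puts 6 subjects in Stage 2a, against 5 in the Protocol.

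**The concern.** Stage 1 may enrol up to 10 subjects to obtain 5 evaluable ones, so a completed Stage 1 has at least five subjects with substantial exposure. Stage 2a, the safety gate for a dose not yet tested in the trial, has no such floor.

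Protocol 7.3 and 7.4 foresee exits that are not DLTs, such as subject judgment, other treatment options, noncompliance, withdrawn consent and loss to follow-up. After escalation the plan is 5 applications at each of 4 visits, 20 in all. A subject who leaves after one application has had 1/20 = 5% of them. Because the DLT period runs from the last application actually given, that subject can complete it. A subject lost before it ends is not excluded either.

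Such a subject can add little to the DLT count but takes one of five places. The error has one direction: the gate opens more easily, and more subjects are then treated at that dose.

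**Working it through.** **The plan's own figure.** The documents state operating characteristics only for the efficacy design (5 then 11 evaluable subjects; go on with 3 or more of 5; succeed with 7 or more of 11). Summing, over x = 3 to 5, P(x responses in 5) × P(at least 7 − x responses in 6) gives 0.0180 at a response rate of 0.30 and 0.9644 at 0.85. Both match the stated 0.018 and 96.44%. No such figure is given for the DLT rule, so it is derived here.

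**Stage 2a gate.** Let k be the number of the 5 subjects with full exposure and p the true DLT rate. Assume that early leavers contribute no DLT. Then

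P(clear) = (1 − p)^k + k·p·(1 − p)^(k−1).

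At p = 0.40:
- k = 5: 0.0778 + 0.2592 = 0.337
- k = 4: 0.1296 + 0.3456 = 0.475
- k = 3: 0.2160 + 0.4320 = 0.648

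| True DLT rate | No leaver | One leaver | Two leavers |
|---|---|---|---|
| 20% | 73.7% | 81.9% | 89.6% |
| One third | 46.1% | 59.3% | 74.1% |
| 40% | 33.7% | 47.5% | 64.8% |
| 50% | 18.8% | 31.3% | 50.0% |

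**Sensitivity to the assumption.** Suppose instead that each subject leaves early with probability d. The DLT probability per subject is p(1 − d) if leavers carry no risk and p(1 − d/2) if they carry half. At p = one third, against 46.1% with no leavers:

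| Assumed d | No risk in leavers | Half risk in leavers |
|---|---|---|
| 10% | 52.8% | 49.4% |
| 20% | 59.8% | 52.8% |
| 30% | 66.8% | 56.3% |

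**Both gates together.** An early leaver is not evaluable for efficacy, so Stage 2b has to make up the place to reach 11 evaluable subjects. Take 11 fully exposed subjects in all, k in Stage 2a and 11 − k in Stage 2b, and require fewer than 3 DLTs in Stage 2b. The Protocol does not say whether Stage 2a DLTs count toward the 3, so both readings are shown.

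Counting Stage 2b only, P(pass both) = P(clear) × P(at most 2 DLTs in 11 − k). At p = 0.40 this is 0.337 × 0.544, 0.475 × 0.420 and 0.648 × 0.315 for k = 5, 4 and 3. Cumulated, it is the sum over x = 0, 1 of P(x DLTs in k) × P(at most 2 − x DLTs in 11 − k).

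| True DLT rate, counting of the 3 DLTs | No leaver | One leaver | Two leavers |
|---|---|---|---|
| One third, Stage 2b only | 31.4% | 33.8% | 34.7% |
| One third, cumulated | 20.5% | 21.7% | 22.5% |
| 40%, Stage 2b only | 18.3% | 20.0% | 20.4% |
| 40%, cumulated | 10.3% | 10.9% | 11.4% |

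The increases run from 0.6 to 3.3 points.

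**With the SAP's 6 subjects.** The mechanism is the same. At one third, 6 fully exposed subjects give 35.1%, and one or two leavers give 46.1% and 59.3%.

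**The case against.** The strongest reply is that the trial does not rest on this gate alone. Stage 2b stops at 3 DLTs, every Stage 2 subject is monitored for DLTs, and Protocol 8.3 lets the regimen be reduced at any time for safety. This largely stands for the final conclusion, as the two-gate table shows. It does not protect the subjects treated in Stage 2b before the limit is reached.

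A reader might infer that leavers also tip the overall tolerability criterion by enlarging its denominator. They cannot do so in an arm that passes both gates and completes. It has at most 1 + 2 = 3 DLTs in at least 11 subjects, or 27%, which is below 33% with or without leavers.

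A reader might also infer that anyone who stops after one patch counts as free of DLT. The Protocol does not support that: under 8.2, a toxicity that prevents three of the four planned applications is itself a DLT. Under the narrower SAP wording, some stops for lower-grade toxicity could count as no DLT.

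The enrolment allowances of 10 for 5 and 21 for 11 are caps and say nothing about expected attrition. One or two leavers in five is an assumption, for a treatment course of only four visits. Nor does early surgery leave the DLT period incomplete, since the period ends at surgery by definition.

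Finally, the line naming Safety Subjects is a flowchart legend, and the images of Figures 3 and 4 were not available here. The tolerability definition in Protocol 6.1 independently supports the same set.

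**Conclusion.** The point holds for subjects who leave Stage 2a early for reasons other than toxicity. As written, each counts fully toward clearing the dose. With no DLT risk in leavers, one leaver raises the chance of clearing by about 13 to 14 percentage points at DLT rates of one third and 40%, and two raise it by about 28 to 31. The number of leavers and their residual risk are assumptions, so the size is uncertain. The direction is not.

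It would go too far to read the rise from 34% to 65% as the added chance that an intolerable dose is finally declared tolerable. That chance moves by about 1 to 3 points once the Stage 2b limit and the 11 evaluable subjects are taken into account. The harm is mainly that Stage 2b opens more often, and more subjects are exposed, at a dose supported by fewer informative subjects than planned. This is a cheap improvement to make in advance.

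**What to change.** First reconcile three pairs of passages:
- the Stage 2a size (5 in Protocol 6.1, 6 in SAP 2.2);
- the DLT criterion for toxicity that prevents planned applications (Protocol 8.2 and SAP 2.10);
- the DLT period in Protocol 8.4 and the adverse event recording in Protocol 9.3.6.6. Recording covers the five pre-surgery visits, then only serious events for 30 days after Visit 5. Visit 5 may fall as early as 72 hours after the last treatment.

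Then, in Protocol 6.1 and SAP 2.2, base the Stage 2a clearance decision on DLT-evaluable subjects. These are anyone with a DLT at any exposure, plus those without a DLT who received at least the existing 75% of the stage dose and were observed through the DLT period (to surgery if that is earlier). Clear the dose only when the planned number of such subjects is available, within the 21-subject cap. Record the exception in Protocol 7.7 and SAP 2.8 and 6.3. Report the DLT proportion on this set beside the Safety Population, which remains the set for all other safety summaries.

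The two-DLT trigger, the target of 11 evaluable subjects and the cap are unchanged. The cost is a definition, one extra table, a possible short delay in Stage 2a when someone leaves, and recording of DLT-relevant events to the end of the DLT period.

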#### **Stopping Rules at Stage 2b:**

If 3 subjects with DLTs, no additional subjects will be dosed.

#### Efficacy Rules at Stage 2b:

Efficacy rules are described in the statistical plans for this stage since it is end of the study.

#### Figure 5. Stage 2b safety and efficacy scheme

*Note:* The surgery is to be performed no later than 42 days post Visit 1.

All subjects will subsequently undergo standard of care, surgical ablation of the tumor and satellite nodes, and possibly additional radiotherapy and chemotherapy. All subjects will be followed for up to 6 months post-surgery at 3 visits: 1 month, 3 months, and 6 months post-surgery for loco-regional response and safety. Follow-up visits may coincide with standard of care follow-up visits, if deemed appropriate by the Principal Investigator.

#### 6.2 Discussion of Trial Design

This study is intended to establish the first-in-human safety and efficacy observations and the optimal dose of the PRV111 (Cisplatin Transmucosal System) prior to the surgical removal of SCC tumors of the oral cavity.

## 7 SELECTION OF SUBJECTS

#### 7.1 Inclusion Criteria

Subjects must meet all of the following inclusion criteria to be eligible for the trial:

- 1. Adult subjects, men and women, defined by age  $\geq 18$  years at the time of screening
- 2. Pathologically proven and clinically confirmed T1 (≤2 cm) or T2 (≥2 cm but ≤4 cm) SCC of the lip or oral cavity (anterior 2/3 of the tongue, floor of mouth, lower and upper gingiva, salivary gland, hard palate, and buccal mucosa)
- 3. Tumor must be easily accessible, with no evidence of infection or active bleeding, encroaching major vessels or clinical evidence of neural invasion. Tumor should not have been previously irradiated
- 4. Tumor must be amenable to surgical resection no later than 42 days post Visit 1
- 5. Clinically and/or radiologically measurable tumor
- 6. Eastern Collaborative Oncology Group Performance Status (ECOG PS) of  $\leq 2$
- Adequate renal function as demonstrated by renal creatinine clearance >50 mL/min (calculated using the Cockcroft-Gault formula)
- Adequate organ function defined as: ANC ≥1000/µL, platelet ≥100,000/µL; Hb ≥9.0 g/dL; AST and ALT ≤2.5 times the upper limit of normal (ULN), serum bilirubin ≤1.5 times the ULN or direct bilirubin ≤ULN for subjects with total bilirubin >1.5 times the ULN
- 9. Candidates for standard of care treatment consisting of surgery
- 10. Male and female subjects of childbearing potential must agree to use 2 methods of effective contraception from Screening during the entire duration of the study and for at least 30 days after the final dose of investigational product. An appropriate birth control is defined as barrier methods with spermicides, oral or parenteral contraceptives and/or intrauterine devices, or naturally or surgically sterile (with documentation in the subject's medical records). Postmenopausal women are defined as presenting at least 12 months' natural spontaneous amenorrhea, or at least 6 weeks following surgical menopause (bilateral oophorectomy). Females of childbearing potential must be non-lactating and have a negative serum hCG within 14 days of treatment initiation
- 11. Absence of any serious underlying medical conditions which could impair the ability of the subject to participate in the study
- 12. Have a life expectancy of >3 months
- 13. Willing and able to provide written informed consent
- 14. Able to return to study site for treatment and follow-up visits as defined in the Protocol

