# 9.2.1 Tumor Photography and Measurements

The primary lesion will be photographed before PRV111 treatment. This will be done to allow for a clinical assessment of response to treatment. For details refer to Study Manual for instructions.

The tumor will be measured in cm to 1 digit to the right of the decimal point using a disposable plastic ruler or caliper. Three dimensions must be recorded (Length x Width x Height).

Note: If tumor or cancerous lesion is flat, a small number (0.05 cm) will be recorded for the Height. If the tumor is a concave, a negative Height is recorded. If the height is an unmeasurable dent, it can be recorded as (-0.05 cm).

The following formula will be used to calculate tumor volume (cm^3)

$$L x W x H x \pi/6$$

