#### PCFB = % tumor volume change from the baseline

Response will be defined as CR, PR or SR. Non-Response will be defined as SD or PD (Table 4).

Table 4. Clinical Response to Treatment Based on Tumor Volume Change\*

Complete Response (CR)	Disappearance of primary lesion.		
Partial Response (PR)	PCFB: ≥30% to 69% decrease in the total tumor volume shrinkage (as determined by clinical measurement, taking as reference the baseline volume.		
Strong Response (SR)	PCFB: ≥70% to 99% decrease in the total tumor volume shrinkage (as determined by clinical measurement, taking as reference the baseline volume.		
Progressive Disease (PD)	PCFB: At least a 20% increase tumor volume as determined by clinical measurement taking as reference the baseline volume (Note: the appearance of one or more new lesions is also considered progression).		
Stable Disease (SD)	Neither sufficient shrinkage to qualify for PR nor sufficient increase to qualify for PD, taking as reference the volume determined by clinical measurement at baseline		

\* Necrosis/inflammation will not be included towards clinical tumor measurements.

9.2.3

Confidential Property of Privo Technologies, Inc. Page 39 of 59

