#### 10.4.2 Evaluable Population

All subjects who have met the inclusion and exclusion criteria, and have completed at least 75% of the total dose required for that stage will be included in the Evaluable Population. This population will be used for the efficacy analysis.

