3.1 PRIMARY: Tumor Photography and Measurements

The primary lesion will be photographed before PRV111 treatment. This will be done to allow for a clinical assessment of response to treatment. For details refer to Study Manual for instructions.

The tumor will be measured in cm to 1 digit to the right of the decimal point using a disposable plastic ruler or caliper. Three dimensions must be recorded (Length x Width x Height).

Note: If tumor or cancerous lesion is flat, a small number (0.05 cm) will be recorded for the Height. If the tumor is a concave, a negative Height is recorded. If the height is an unmeasurable dent, it can be recorded as (-0.05 cm). The volume calculations use the heights absolute value. The following formula will be used to calculate tumor volume (cm³)

$$L \times W \times H \times \pi/6$$

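### Criterion 5 accepts a tumor measurable only on imaging, but the primary response compares clinical volumes at Visits 1 and 5, so such a subject is evaluable without a like-for-like outcome

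*Protocol*

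**What the plan says.** **Entry.** Criterion 5 (Protocol 7.1, the synopsis and SAP 2.4.1) requires a "Clinically and/or radiologically measurable tumor". Either method alone satisfies it.

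**Measurement.** SAP 3.1 states: "The tumor will be measured in cm to 1 digit to the right of the decimal point using a disposable plastic ruler or caliper". Protocol 9.2.1 has the same rule. Both require three dimensions and compute volume as L x W x H x π/6. For height there is an allowance: "If tumor or cancerous lesion is flat, a small number (0.05 cm) will be recorded for the Height". An unmeasurable dent gets -0.05 cm, and the SAP uses the absolute value.

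**Response.** In Protocol Table 4, partial and strong response are set "as determined by clinical measurement, taking as reference the baseline volume". Stable disease is judged "taking as reference the volume determined by clinical measurement at baseline", and progression by volume uses the same basis. Complete response is the lesion's disappearance, with no method named. SAP 3.1.2 bases the final determination on the change from Visit 1 to Visit 5 and calls the study a success with at least 7 responders among up to 11 evaluable subjects.

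**Evaluability.** Under Protocol 10.4.2, subjects who meet the entry criteria and "have completed at least 75% of the total dose required for that stage will be included in the Evaluable Population". SAP 5.2.2 agrees, defining 75% as three of four visits. Neither asks for a clinical volume at both visits.

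**Missing baseline.** SAP 5.2.3 replaces a missing Visit 1 tumor measurement with the screening CT. SAP 6.2 uses the next earliest available data point. SAP 6.2 also says both that unretrievable efficacy data will be imputed and that no imputation will be applied.

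**The concern.** Eligibility and the primary endpoint use different standards of measurability, and nothing between them closes the gap. A subject admitted on imaging alone can complete the required visits, enter the Evaluable Population and count towards the 11 without a clinical Visit 1 volume to compare with Visit 5.

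What happens next depends on which SAP sentence is followed. Section 5.2.3 gives a CT baseline set against a clinical follow-up. Section 6.2 can be read as taking Visit 2 as baseline, which is after the first treatment. The imputation statements then leave open whether a subject with no usable change is a non-responder or simply missing.

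The success rule is a fixed count of 7, so one misclassified subject moves the error rates noticeably. If the subject falls in Stage 1, the same misclassification feeds the rule that decides between keeping and escalating the dose.

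**Working it through.** **Inputs.** From Protocol 10.2: null rate 0.30, alternative 0.85, n1 = 5, r1 = 2, N = 11, R = 6, type I error 0.018, power 96.44%. (One sentence in SAP 5.1 attaches that power to a rate of 0.65; its own table says 0.85, which is used here.) The documents do not say how many imaging-only subjects would enroll, so one and two are assumed.

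**Plan's own figures.** Let b(n,x,p) be the binomial probability of x responses and T(n,k,p) the chance of k or more. The design rejects with probability Σ over x = 3 to 5 of b(5,x,p) · T(6,7-x,p).

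At p = 0.30: 0.1323 × 0.0705 + 0.0284 × 0.2557 + 0.0024 × 0.5798 = 0.0180. At p = 0.85 the sum is 0.9644. Both stated figures are reproduced.

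**One false responder.**
- In Stage 1: Σ over x = 2 to 4 of b(4,x,0.30) · T(6,6-x,0.30) = 0.0427.
- In Stage 2: Σ over x = 3 to 5 of b(5,x,0.30) · T(5,6-x,0.30) = 0.0370.

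**One subject counted as a non-response, or left out with both cut-offs kept.**
- In Stage 1: Σ over x = 3 to 4 of b(4,x,0.85) · T(6,7-x,0.85) = 0.870.
- In Stage 2: Σ over x = 3 to 5 of b(5,x,0.85) · T(5,7-x,0.85) = 0.939.

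Two subjects follow in the same way:

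| Affected subjects | Type I error if false responders | Power at 0.85 if non-responses or left out |
|---|---|---|
| None | 0.018 | 96.4% |
| One, Stage 1 | 0.043 | 87.0% |
| One, Stage 2 | 0.037 | 93.9% |
| Two, both Stage 1 | 0.095 | 58.5% |
| Two, one in each stage | 0.086 | 81.6% |
| Two, both Stage 2 | 0.070 | 85.9% |

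**Changed-dose path.** If the dose changes after Stage 1 and 11 new subjects are tested in a single stage, T(11,7,0.30) = 0.0216. With one false responder it is T(10,6,0.30) = 0.0473. Power at 0.85 falls from T(11,7,0.85) = 0.984 to T(10,7,0.85) = 0.950 with one lost response.

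**Stage 1 dose decision.** At a true rate of 0.30, the chance of 3 or more responses in 5 is T(5,3,0.30) = 0.163. With one false responder it is T(4,2,0.30) = 0.348.

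**How a mixed-method comparison can create a response.** Assume a lesion of 2.0 x 1.5 cm by both methods, with a CT height of 0.5 cm at baseline and a clinical height of 0.05 cm (recorded as flat) at Visit 5. The volumes are 2.0 × 1.5 × 0.5 × π/6 = 0.785 cm³ and 2.0 × 1.5 × 0.05 × π/6 = 0.0785 cm³. The percent change is -90%, a strong response with no true change. With a CT height of 0.1 cm the change is -50%, a partial response. These dimensions are illustrative; the documents do not say how CT and ruler heights compare.

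**The case against.** The strongest reply is that the problem subject hardly exists. Criterion 2 requires a tumor that is "Pathologically proven and clinically confirmed T1" or T2, stages defined by size in cm. Criterion 3 says "Tumor must be easily accessible, with no evidence of infection or active bleeding". The patch is placed on the lesion, one or two are used according to tumor size, the lesion is photographed, and Visit 1 includes a clinical tumor measurement before dosing. The assigned heights give a flat or dented lesion a nonzero volume. This stands as an argument about frequency. It does not close the gap: neither criterion requires a recordable length and width, and the height rule supplies only the third dimension.

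A reader might infer that an imaging-only subject becomes an automatic complete response. The documents do not support that. No passage equates a missing clinical measurement with disappearance, and a lesion never clinically visible cannot be observed to disappear. A false response is possible, not automatic.

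A reader might also infer that the plan offers no percent change at all for such a subject. It does, through the CT baseline in SAP 5.2.3; the difficulty is that the two ends of the comparison then use different methods.

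Finally, some schedule rows and efficacy subsections are redacted and may describe imaging. No conclusion is drawn here about radiological assessments. The visible response definitions for shrinkage, stability and volume growth still rest on clinical measurement.

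**Conclusion.** The mismatch is real and limited. A subject may enter on imaging alone and be evaluable without a like-for-like Visit 1 to Visit 5 clinical volume, and the SAP does not settle how that subject is scored. Followed as written, the CT substitution can yield a false response.

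Under the stated two-stage design, one false responder roughly doubles the type I error or slightly more, and two raise it to 0.070-0.095. Counted as non-responses or left out, one such subject costs about 3 to 9 percentage points of power at 0.85, and two cost about 11 to 38. The ranges reflect the stage in which the subjects fall.

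All of this is conditional on one or two such subjects among 11, which is an assumption, and the other entry criteria suggest that the number will usually be zero. A starting type I error of 0.022 applies only to the changed-dose path; it should not be read as the error of the stated two-stage design. The case for acting is that a single subject can matter at this sample size and the correction is small.

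**What to change.** In Protocol 7.1, the synopsis and SAP 2.4.1, reword criterion 5 along these lines: *Clinically measurable tumor: length and width recordable by ruler or caliper at Visit 1 before dosing, with height measured or assigned under the flat/dent rule (0.05 or -0.05 cm).* Add that imaging may be recorded as well but does not meet the criterion alone. Naming the assigned heights matters, because a bare requirement for three measurable dimensions could be read as excluding the flat and dented lesions that the plan deliberately admits.

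In SAP 5.2.3 and 6.2, remove the screening-CT substitution for the primary response so that Visits 1 and 5 use the same clinical method. Reconcile the two baseline fallbacks, and replace the conflicting imputation sentences with one rule for counting an evaluable subject who lacks a valid clinical pair.

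The cost is one eligibility line in three places and short edits to two SAP sections. With all 11 outcomes valid, the design keeps its stated type I error of 0.018 and power of 96.44%. The downside is that the few subjects with tumors measurable only on imaging are not enrolled.
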